4.2. Scientific Rationale for Study Design

In order to allow each participant to act as his/her own control for safety and PK comparisons, a 3-period crossover design has been selected. This study will also be open label as the study primary endpoint PK measures are objective rather than subjective.

Conducting the study in healthy adult participants mitigates the potential confounding effects of the disease state and concomitant medications in participants with metastatic RET fusion-positive NSCLC, advanced or metastatic RET-mutant MTC, or advanced or metastatic RET fusion-positive thyroid cancer. A population of healthy participants is frequently used in the assessment of the PK of both small and large molecules.

The doses, participant population, study duration, and sample collection timing are considered adequate to achieve the study objectives.

4.3. Justification for Dose

Dose being used is representative of the typical dose size to be used in pediatric studies. As the PK of selpercatinib have been demonstrated to be linear in the dose range of CCI in adult cancer patients, results from study JZJU can be expected to be applicable across the therapeutic dose range.

4.4. End of Study Definition

A participant is considered to have completed the study if he/she has completed all required periods of the study including the last visit or the last scheduled procedure shown in the SoA.

The end of the study is defined as the date of the last visit of the last participant in the study.

5. Study Population

Eligibility of participants for enrollment in the study will be based on the results of screening medical history, physical examination, vital signs, clinical laboratory tests, and ECG.

The inclusion and exclusion criteria used to determine eligibility should be applied at screening only, and not continuously throughout the study. Clinical laboratory assessments and vital signs may be repeated from screening through Day -1 at the discretion of the investigator in order to confirm eligibility.

Screening may occur up to 28 days prior to enrollment. Participants who are not enrolled within 28 days of screening may undergo an additional medical assessment and/or clinical measurements to confirm their eligibility. In such instances, the following screening tests and procedures should be repeated: clinical laboratory assessments and vital signs.

Prospective approval of protocol deviations to recruitment and enrollment criteria, also known as protocol waivers or exemptions, is not permitted.

5.1. Inclusion Criteria

Participants are eligible to be included in the study only if all of the following criteria apply:

Age

1. Participant must be 18 to 65 years of age, inclusive, at the time of signing the informed consent form (ICF).

Type of Participant and Disease Characteristics

2. Participants who are overtly healthy as determined by medical evaluation including medical history, physical examination, and vital signs.
3. Participants who have clinical laboratory test results within the normal reference range for the population or investigative site, or results with acceptable deviations that are judged to be not clinically significant by the investigator.
4. Participants who have venous access sufficient to allow for blood sampling as per the protocol.

Weight

5. Have a body mass index within the range 18.0 to 35.0 kg/m² (inclusive).

Sex and Contraceptive/Barrier Requirements

6. Male or female participants - contraceptive use by men or women should be consistent with local regulations regarding the methods of contraception for those participating in clinical studies.
 - a. Male participants:
 - Are not required to adhere to contraceptive requirements.

b. Female participants:

- Female participants of childbearing potential (see Appendix 4 [Section 10.4]) who are abstinent (if this is complete abstinence, as their preferred and usual lifestyle) or in a same-sex relationship (as part of their preferred and usual lifestyle) must agree to either remain abstinent or stay in a same-sex relationship without sexual relationships with males.
Periodic abstinence (e.g., calendar, ovulation, symptothermal, post-ovulation methods), declaration of abstinence just for the duration of a study, and withdrawal, are not acceptable methods of contraception.
- Female participants of childbearing potential, who are not abstinent as described above, must agree to use a highly effective method of contraception (that is, one with less than 1% failure rate) such as combination oral contraceptives, implanted/injected contraceptives, intrauterine devices, or sterile partner until 30 days after the last dose of study medication.
- Female participants not of childbearing potential are not required to use contraception. This includes females who are:
 - Infertile due to surgical sterilization (hysterectomy, bilateral oophorectomy, bilateral salpingectomy, bilateral tubal occlusion, or bilateral tubal ligation), or congenital anomaly (for example, Müllerian agenesis)
 - Postmenopausal as defined in Appendix 4 (Section 10.4).

Informed Consent

7. Capable of giving signed informed consent as described in Appendix 1 (Section 10.1), which includes compliance with the requirements and restrictions listed in the ICF and in this protocol.

5.2. Exclusion Criteria

Participants are excluded from the study if any of the following criteria apply:

Medical Conditions

1. Have a positive pregnancy test at screening or Day -1, where applicable.
2. Are planning to become pregnant during the study or within 1 month of study completion.
3. Are women who are lactating.
4. Have known allergies to selpercatinib-related compounds or any components of the formulation of selpercatinib, or history of significant atopy.
5. Have a history of allergic reactions to medications or food products.
6. Have a clinically significant abnormality of blood pressure and/or pulse rate as determined by the investigator.
7. Clinically significant abnormalities on ECG as determined by the investigator or prolongation of the corrected QT interval using or Fridericia's formula (QTcF) >450 msec at screening.

8. Have clinically significant active cardiovascular disease or history of myocardial infarction within 6 months prior to the planned start of selpercatinib.
9. Have a history or presence of cardiovascular, respiratory, renal, gastrointestinal, endocrine, hematological, or neurological disorders capable of significantly altering the absorption, metabolism, or elimination of drugs; of constituting a risk when taking the investigational product; or of interfering with the interpretation of data. Appendectomy, uncomplicated hernia, splenectomy, and cholecystectomy are considered as acceptable.
10. Have a creatinine clearance <60 mL/min, as calculated using the Chronic Kidney Disease Epidemiology Collaboration (CKD-EPI) equation (Levey et al, 2009).
$$\text{eGFR} = 141 \times \min(\text{Scr}/\text{K}, 1)^\alpha \times \max(\text{Scr}/\text{K}, 1)^{-1.209} \times 0.993^{\text{age}}$$
$$\times 1.018 \text{ (if female)}$$
$$\times 1.159 \text{ (if black)}$$
11. Show a history of central nervous system conditions such as strokes, transient ischemic attacks, significant head trauma, seizures, central nervous system infections, migraine, brain surgery, or any other neurological conditions that, in the opinion of the investigator, increase the risk of participating in the study.
12. Have a history or presence of neuropsychiatric disease (e.g., bipolar disorder, schizophrenia, depression) considered as clinically significant by the investigator.
13. Regularly use known drugs of abuse or show positive findings on drug screening.
14. Show evidence of human immunodeficiency virus infection and/or positive human immunodeficiency virus antibodies.
15. Presence of hepatitis B surface antigen at screening or within 3 months prior to first dose of study intervention.
16. Positive hepatitis C antibody test result at screening or within 3 months prior to first dose of study intervention.
NOTE: Participants with positive hepatitis C antibody due to prior resolved disease can be enrolled if a confirmatory negative hepatitis C RNA test is obtained.
17. Positive hepatitis C RNA test result at screening or within 3 months prior to first dose of study intervention.
NOTE: Test is optional and participants with negative hepatitis C antibody test are not required to also undergo hepatitis C RNA testing.
18. Have donated blood of more than 500 mL within the previous 3 months of study screening.
19. Have any medical conditions, medical history, or are taking any medications that are contraindicated in the selpercatinib label.

■

20. Have participated, within the last 30 days of admission, in a clinical study involving an investigational product. If the previous investigational product has a long half-life, 5 half-lives or 30 days (whichever is longer) should have passed.
21. Have previously completed or withdrawn from this study or any other study investigating selpercatinib, and have previously received the investigational product.

22. Use of H₂ blockers, proton-pump inhibitors, and other antacids within 7 days of screening.
23. Are intending to use over-the-counter or prescription medication, including dietary supplements, within 14 days prior to dosing and until study discharge (apart from occasional acetaminophen (≤ 2 g/24 hours), hormonal contraception, or hormone-replacement therapy).
- P**
24. Are currently enrolled in any other clinical study involving an investigational product or any other type of medical research judged not to be scientifically or medically compatible with this study
- D**
25. Have an average weekly alcohol intake that exceeds 21 units per week (males) and 14 units per week (females); 1 unit = 12 oz or 360 mL of beer; 5 oz or 150 mL of wine; 1.5 oz or 45 mL of distilled spirit(s)
26. Are unwilling to stop alcohol consumption 48 hours prior to each admission to the CRU, and while resident at the CRU. At all other times, participants must agree to consume no more than 2 units per day
27. Are smokers of more than 10 cigarettes or e-cigarettes, or 3 cigars or 3 pipes, per day and are unable to refrain from smoking while resident at the CRU
28. Consume excessive amounts of coffee, tea, cola, or other caffeinated beverages per day, or are unwilling to stop caffeine consumption 48 hours prior to admission and while resident at the CRU. Excessive amount is defined as greater than 6 servings (1 serving is approximately equivalent to 120 mg of caffeine).
29. Are unable to consume a standard meal.
30. Currently use or show evidence of substance abuse (including alcohol abuse) or dependence within the past 6 months based on medical history at screening visit
31. Inability to comply with the dietary regimen of the CRU
32. Are Lilly employees or are an employee of any third party involved in the study who require exclusion of their employees
33. Are investigator site personnel directly affiliated with this study and/or their immediate families. Immediate family is defined as a spouse, parent, child, or sibling, whether biological or legally adopted
34. In the opinion of the investigator or sponsor, are unsuitable for inclusion in the study

5 **█**

Throughout the study, participants may undergo medical assessments and review of compliance with requirements before continuing in the study.

5.3.1. Meals and Dietary Restrictions

During the confinement period, participants will consume only food and beverages that are provided to them by the CRU staff. Standard meals (e.g., breakfast, lunch, dinner, and snack) will be provided to the participants while resident at the CRU.

Selpercatinib will be dosed in the fasted state on Days 1, 8, and 15. On these dosing occasions, the participants will be fasted overnight (at least 10 hours) prior to dosing and refrain from consuming water from 1 hour predose until 2 hours postdose, excluding the amount of water consumed at dosing. Food is allowed from 4 hours postdose. At all other times during the study, participants may consume water ad libitum.

5.3.2. Caffeine, Alcohol, and Tobacco

Participants will abstain from ingesting caffeine- or xanthine-containing products (e.g., coffee, tea, cola drinks, and chocolate) for 48 hours prior to admission until after discharge from the study.

Participants will abstain from alcohol for 48 prior to admission until after discharge from the study.

Participants who use tobacco products will be instructed that use of nicotine-containing products (including nicotine patches) will not be permitted while they are in the clinical unit.

5.3.3. Activity

Participants will abstain from strenuous exercise for 48 hours before each blood collection for clinical laboratory tests. Participants may participate in light recreational activities during the study (e.g., watching television, reading).

5.4. Screen Failures

Screen failures are defined as participants who consent to participate in the clinical study but are not subsequently assigned to study intervention.

Individuals who do not meet the criteria for participation in this study (screen failure) may not be rescreened. Repeating of laboratory tests during the screening period or repeating screening tests to comply with the protocol-designated screening period does not constitute rescreening.

6. Study Intervention(s) and Concomitant Therapy

Study intervention is defined as any investigational intervention(s), marketed product(s), placebo, or medical device(s) intended to be administered to/used by a study participant according to the study protocol.

6.1. Study Intervention(s) Administered

Table JZJU.1. Study Interventions Administered

Arm Name	Capsule	Ready to use	PFOS
Study Intervention	Selpercatinib	Selpercatinib	Selpercatinib
Dosage Formulation	Capsule	Suspension	Suspension
Unit dose strengths/Dosage Levels	1 × 20-mg capsule	20 mg/mL	20 mg/mL
Route of Administration	Oral	Oral	Oral
Dosing Instructions	1 capsule taken on Day 1, 8, or 15, according to the randomization schedule	1 mL taken on Day 1, 8, or 15, according to the randomization schedule	1 mL taken on Day 1, 8, or 15, according to the randomization schedule

Abbreviations: PFOS = powder for oral suspension.

6.1.1. Administration Details

A single oral dose of selpercatinib 20 mg will be administered in the morning of Days 1, 8, and 15. Capsules and suspension of selpercatinib will be administered with approximately 240mL of room-temperature water. All doses will be administered while in a sitting position. Participants will not be allowed to lie supine for 2 hours after dosing, unless clinically indicated or for study procedures.

Selpercatinib capsules should be swallowed whole. Participants should not break, empty, or chew the capsules.

Further instructions will be provided.

On dosing days, participants will adhere to meal restrictions as outlined in Section 5.3.1.

6.2. Preparation, Handling, Storage, and Accountability

1. The investigator or designee must confirm appropriate storage conditions have been maintained during transit for all study intervention received and any discrepancies are reported and resolved before use of the study intervention.
2. Only participants enrolled in the study may receive study intervention. Only authorized study personnel may supply, prepare, or administer study intervention. All study intervention must be stored in a secure, environmentally controlled, and monitored

(manual or automated) area in accordance with the labeled storage conditions with access limited to the investigator and authorized study personnel.

3. The investigator or authorized study personnel are responsible for study intervention accountability, reconciliation, and record maintenance (i.e., receipt, reconciliation, and final disposition records).
4. Further guidance and information for the final disposition of unused study interventions are provided in the study reference manual.

Note: in some cases, sites may destroy the material if the evaluator has verified and documented that the site has appropriate facilities and written procedures to dispose of clinical materials.

Samples of the specific batches of selpercatinib used in the study will be retained; details will be provided separately.

6.3. Measures to Minimize Bias: Randomization and Blinding

This is an open-label study. There is no bias as the primary endpoint is PK and objective in measure.

Participants will be assigned a unique number (randomization number) on Day 1. The randomization number encodes the participant's assignment to be dosed with either the capsule, RTU suspension, or PFOS on Days 1, 8, and 15, according to the randomization schedule generated prior to the study by the Statistics Department at Covance.

6.4. Study Intervention Compliance

Participants are dosed at the site and will receive study intervention directly from the investigator or designee, under medical supervision. The date and time of each dose administered in the clinic will be recorded in the source documents and recorded in the electronic case report form (eCRF). The dose of study intervention and study participant identification will be confirmed at the time of dosing by a member of the study site staff other than the person administering the study intervention. Study site personnel will examine each participant's mouth to ensure that the study intervention was ingested.

When the individual dose for a participant is prepared from a bulk supply, the preparation of the dose will be confirmed by a second member of the study site staff.

6.5. Dose Modification

Dose modification will not be permitted in this study.

6.6. Continued Access to Study Intervention After the End of the Study

Selpercatinib will not be made available to participants after completion of the study.

6.7. Treatment of Overdose

For the purposes of this study, an overdose of selpercatinib is considered as any dose higher than the dose assigned. There is no specific antidote for selpercatinib.

In the event of an overdose, the investigator/treating physician should:

1. Contact the medical monitor immediately.
2. Closely monitor the participant for any AEs/serious adverse events (SAE) and laboratory abnormalities until study intervention can no longer be detected systemically (at least 5 days).
3. Document the quantity of the excess dose as well as the duration of the overdose in the eCRF.

Decisions regarding dose interruptions will be made by the investigator in consultation with the medical monitor based on the clinical evaluation of the participant.

6.8. Concomitant Therapy

Any medication or vaccine (including over-the-counter or prescription medicines, vitamins, and/or herbal supplements) that the participant is receiving at the time of enrollment or receives during the study must be recorded along with:

- a. Reason for use
- b. Dates of administration including start and end dates
- c. Dosage information including dose and frequency for concomitant therapy of special interest

The medical monitor should be contacted if there are any questions regarding concomitant or prior therapy.

Participants must abstain from taking prescription or nonprescription drugs (including vitamins and dietary or herbal supplements) within 14 days before the start of study intervention until discharge from the study.

Acetaminophen, at doses of ≤ 2 grams/24 hours, is permitted for use at the discretion of the investigator for the treatment of headache, etc. Contraceptive medication is permitted as per the contraception requirements (Appendix 4 [Section 10.4]), and hormone-replacement therapy is also allowed.

Other medication may be considered on a case-by-case basis by the investigator in consultation with the Lilly clinical pharmacologist (CP)/clinical research physician (CRP), or designee.

7. Discontinuation of Study Intervention and Participant Discontinuation/Withdrawal

Participants discontinuing from the study or study intervention prematurely for any reason should complete AE and other early discontinuation procedures as per the SoA (Section 1.3).

Discontinuation of the study as a whole is described in Appendix 1 (Section 10.1).

[figure not shown]
7.1. Discontinuation of Study Intervention

In rare instances, it may be necessary for a participant to permanently discontinue study intervention. If study intervention is permanently discontinued, the participant will remain in the study to be evaluated for safety. See the SoA for data to be collected at the time of discontinuation of study intervention and discharge from the study, and for any further evaluations that need to be completed.

7.1.1. Liver Chemistry Stopping Criteria

Study intervention will be discontinued **for a participant** if liver chemistry stopping criteria are met.

Phase 1 Liver Chemistry Stopping Algorithm

Abbreviations: ALT = alanine transaminase; INR = international normalized ratio; SAE = serious adverse event; ULN = upper limit of normal.

Liver Safety: Suggested Actions and Follow-up Assessments can be found in Appendix 6 (Section 10.6).

7.1.2. QTc Stopping Criteria

A participant who meets either bulleted criterion following single ECG assessment should have ECG repeated. If the participant still meets either bulleted criterion they will be withdrawn from the study.

- QTc, QTcB, or QTcF >500 msec
- Change from baseline: QTc >60 msec

If a clinically significant finding is identified (including, but not limited to changes from baseline in QTcB or QTcF) after enrollment, the investigator or qualified designee will determine if the participant can continue in the study and if any change in participant management is needed. This review of the ECG printed at the time of collection must be documented. Any new clinically relevant finding should be reported as an AE.

See the SoA for data to be collected at the time of intervention discontinuation and discharge from the study, and for any further evaluations that need to be completed.

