7.2. Participant Discontinuation/Withdrawal from the Study

A participant may withdraw from the study:

- at any time at his/her own request
- at the discretion of the investigator for safety, behavioral, compliance, or administrative reasons
- if the participant becomes pregnant during the study
- if enrolled in any other clinical study involving an investigational product or enrolled in any other type of medical research judged not to be scientifically or medically compatible with this study
- if the participant, for any reason, requires treatment with another therapeutic agent that has been demonstrated to be effective for treatment of the study indication, discontinuation from the study occurs prior to introduction of the new agent.

Discontinuation is expected to be uncommon.

At the time of discontinuing from the study, if possible, an early discontinuation visit should be conducted, as shown in the SoA. See SoA for data to be collected at the time of study discontinuation and for any further evaluations that need to be completed. The participant will be permanently discontinued from both the study intervention and the study at that time.

If the participant withdraws consent for disclosure of future information, the sponsor may retain and continue to use any data collected before such a withdrawal of consent. If a participant withdraws from the study, he/she may request destruction of any samples taken and not tested, and the investigator must document this in the site study records.

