8.2.2. Vital Signs

For each participant, vital signs measurements should be conducted according to the SoA (Section 1.3).

Blood pressure and pulse rate should be measured singly after at least 5 minutes supine. For each individual participant, the same cuff size should be used throughout the study for the measurements of blood pressure. The cuff should be attached to the participant's dominant arm.

Unscheduled orthostatic vital signs should be assessed, if possible, during any AE of dizziness or posture-induced symptoms. Where orthostatic measurements are required, participants should be supine for at least 5 minutes and then participants will stand, and standing blood pressure will be measured after 2 minutes, but no longer than 3 minutes. If the participant feels unable to stand, supine vital signs only will be collected. Additional vital signs may be measured if warranted.

8.2.3. *Electrocardiograms*

For each participant, single 12-lead ECGs will be obtained as outlined in the SoA (see Section 1.3). Refer to Section 7 for QTc withdrawal criteria and any additional QTc readings that may be necessary.

Electrocardiograms must be recorded before collecting any blood samples. Participants must be supine for approximately 5 to 10 minutes before ECG collection and remain supine but awake during ECG collection. Electrocardiograms may be obtained at additional times, when deemed clinically necessary. All ECGs recorded should be stored at the investigational site.

Electrocardiograms will be interpreted by the investigator at the site as soon after the time of ECG collection as possible, and ideally while the participant is still present, to determine whether the participant meets entry criteria at the relevant visit(s) and for immediate participant management, should any clinically relevant findings be identified.

If a clinically significant finding is identified (including, but not limited to, changes in QT/QTc interval from baseline) after enrollment, the investigator will determine if the participant can continue in the study. The investigator, or qualified designee, is responsible for determining if any change in participant management is needed and must document his/her review of the ECG printed at the time of collection. Any new clinically relevant finding should be reported as an AE.

8.2.4. *Clinical Safety Laboratory Tests*

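### Protocol 7.1 keeps a participant in the study after study intervention is stopped, but its subsection 7.1.2 withdraws a participant with a confirmed QTc criterion from the study, and no exception is stated

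*Protocol*

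**What the plan says.** Protocol 7.1 deals with permanent discontinuation of study intervention and gives the consequence without qualification: "If study intervention is permanently discontinued, the participant will remain in the study to be evaluated for safety".

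Protocol 7.1.2 is a subsection of 7.1. It lists two triggers, "QTc, QTcB, or QTcF >500 msec" and "Change from baseline: QTc >60 msec", and asks for a repeat ECG when either is met. It then states: "If the participant still meets either bulleted criterion they will be withdrawn from the study". It closes with a pointer to the Schedule of Activities: "See the SoA for data to be collected at the time of intervention discontinuation and discharge from the study". Protocol 8.2.3 refers back to the same rule: "Refer to Section 7 for QTc withdrawal criteria".

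Protocol 7.2 defines what leaving the study means: "The participant will be permanently discontinued from both the study intervention and the study at that time". Its list of reasons does not name the QTc criteria, although it allows the investigator to withdraw someone on safety grounds.

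The neighbouring liver rule, 7.1.1, stops study intervention "if liver chemistry stopping criteria are met" and says nothing about leaving the study.

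The SAP does not address study status after a stopping criterion.

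**The concern.** A site that confirms a QTc criterion needs to know whether the participant is off study drug or off study. The protocol treats these as different statuses: Section 7 opens by naming both, and 8.3.2 distinguishes them for pregnancy. For this trigger it gives both answers.

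Two things depend on the answer. One is whether the safety assessments still scheduled after the dose already given are carried out as study procedures. The other is the date on which routine adverse event collection ends, because the table in Protocol 8.3.1 ties it to the end of study participation. The secondary safety endpoint in Protocol Section 3 is a summary of treatment-emergent and serious adverse events, so two sites or monitors reading the text differently would observe such a participant for different lengths of time.

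**Working it through.** The plan states no figure on this point, so the check is a comparison of the text.

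| Protocol section | Trigger | Study intervention | Study participation |
|---|---|---|---|
| 7.1 | Permanent discontinuation of intervention, any cause | Stopped | Continues, for safety evaluation |
| 7.1.1 | Liver chemistry criteria | Stopped | Not mentioned, so 7.1 governs |
| 7.1.2 (and 8.2.3) | QTc criterion confirmed on repeat ECG | Stopped, by withdrawal | Ends |
| 7.2 | Leaving the study | Stopped | Ends |

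**Step 1: do 7.1 and 7.1.2 cover the same event?** Yes, while doses remain. Withdrawal under 7.1.2 means, by 7.2, that study intervention is permanently discontinued. That is the condition in 7.1, whose consequence is that the participant stays. The closing pointer in 7.1.2 also describes the event as discontinuation of intervention together with discharge. After the Day 15 dose there is no dosing left to stop, so 7.1 is strictly engaged only by triggers before that dose.

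**Step 2: is an exception stated?** No. Neither 7.1, 7.1.2, 7.2 nor 8.2.3 says that the QTc rule overrides the general one.

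**Step 3: what is the same on either reading?**
- The opening of Section 7 requires early discontinuation procedures whether the participant leaves the study or only the intervention. The early discontinuation column of the Schedule of Activities includes an ECG.
- 7.1, 7.1.2 and 7.2 all allow for further evaluations beyond that visit.
- 8.3 keeps the investigator responsible for following events that led to discontinuation of either kind, and 10.3.4 requires supplemental evaluation where medically indicated.
- 8.3.1 provides for reporting serious events learned of after participation ends.

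**Step 4: what differs?**
- Assessments already scheduled after a dose, such as vital signs and laboratory tests at 24 h, vital signs on Day 5, 12 or 19, and the Day 21 assessments.
- The end of routine adverse event collection. Assume that withdrawal takes effect on the day of confirmation, and that remaining in the study means staying to Day 21. The two readings then differ by 21 − 1 = 20 days for a Day 1 trigger, 21 − 8 = 13 days for a Day 8 trigger, and 21 − 15 = 6 days for a predose Day 15 trigger. The protocol does not say how long a participant who remains would be followed, so these are upper figures for in-study observation.

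**Step 5: context from the stated half-life.** Protocol 2.2 gives about 32 h. Five half-lives are 5 × 32 = 160 h, and 160 / 24 = 6.7 days. A dose given before a postdose trigger is therefore still being eliminated over much of the following week. This shows why the status matters for a dose already given. It does not measure how often the problem arises.

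**The case against.** The strongest reply is that a specific rule displaces a general one. On that view 7.1 is the default and 7.1.2 is a stricter rule for one trigger. Section 8.2.3 calls these withdrawal criteria, and 7.2 permits withdrawal for safety, so three sections line up. This reading is coherent and may be what was intended. But the protocol does not say so, 7.1.2 sits under the very rule it would override, and the liver rule beside it stops intervention only. (That contrast rests on the sentence in 7.1.1, since the liver algorithm figure was not available for this review.) A site should not have to infer a participant's status after a confirmed stopping criterion.

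A second reply is that follow-up is largely secured either way. Step 3 shows that this is right, and it limits the point.

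A reader might infer more than the documents support:

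- *Follow-up shrinks to one exit visit.* Both 7.1.2 and 7.2 allow for further evaluations, and the duty in 8.3 continues.
- *The participant leaves near peak exposure.* No passage says so. ECGs are scheduled predose as well as at 2 h on Days 1, 8 and 15, and again on Day 21. The predose ECGs on Days 8 and 15 fall 7 × 24 = 168 h after the previous dose, past the 160 h above, and the Day 21 ECG falls about 6 × 24 = 144 h after the last dose. Only a 2 h trigger is close to the stated median peak time of about 2 h.
- *A primary-endpoint profile is lost because of the contradiction.* Section 7.1 promises continued safety evaluation, not continued pharmacokinetic sampling. Profiles already completed stay usable, because the pharmacokinetic population needs only one dose and evaluable data. Enrolling about 42 for 36 completers leaves room for 42 − 36 = 6 losses.
- *This is the gravest ECG finding in the study.* The protocol lists two QTc criteria and does not rank ECG findings.

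**Conclusion.** The contradiction is real: for a confirmed QTc criterion, 7.1 keeps the participant in the study and 7.1.2 takes the participant out, with no stated exception. It is wrong as written and of minor severity. Its reach is limited to the remaining scheduled safety assessments and the stop date of routine adverse event collection for a dose already given. The view that few participants would be affected is a judgement. The documents give no QTc trigger rate, but Protocol 7.2 expects discontinuation to be uncommon and the study enrols only about 42 healthy participants at a single 20 mg dose level. The sample size, the mixed model and the analysis populations are untouched. No view is taken here on which of the two rules is clinically right.

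**What to change.** Reconcile Protocol 7.1, 7.1.2, 7.2 and 8.2.3 so that they give one study status after a confirmed QTc criterion. The text should state:

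- whether the criterion ends study intervention or study participation and, if 7.1.2 is meant as an exception, say so in 7.1;
- whether safety assessments already scheduled for the dose given continue;
- when routine adverse event collection stops for such a participant, in line with the table in 8.3.1.

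The sponsor's medical team decides which status applies. The cost is a wording amendment and, at most, completion of assessments already on the schedule for a participant resident in the unit. The statistical methods in the SAP need no change.
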